2. INTRODUCTION

This Statistical Analysis Plan (SAP) details the statistical analyses for the REN001-201 (STRIDE) study and the sub-study REN001-201-DXA. REN001-201 is a 24-week double blind, randomized placebo-controlled study, designed to assess the efficacy and safety of mavodelpar (REN001) in patients with Primary Mitochondrial Myopathy (PMM). REN001-201-DXA is an exploratory sub-study to REN001-201, designed to assess changes in bone mineral density (BMD), using Dual Energy X-ray Absorptiometry (DXA) scans, after 24 weeks of treatment with mavodelpar.

The purpose of this SAP is to ensure that the data listings, summary tables and figures which will be produced, and the statistical methodologies that will be used, are comprehensive and appropriate for the assessment of study objectives specified in the study protocols. Changes from the analyses specified in the protocol will be identified in the SAP and any amendments to the SAP will be made prior to database lock. Any additional analyses not described in the final SAP or deviations from the final SAP will be documented in the clinical study report (CSR).

The SAP has been developed based on REN001-201 Protocol Version 4.0, REN001-201-DXA Protocol Version 2.0 and the latest CRF available (Version 5.0, Date 17 November 2021). The subsequent country specific protocol amendments for REN001-201 (see Appendix 2) do not impact the SAP.

The analysis of this study will occur after all subjects have had the ability to complete REN001-201 and the REN001-201-DXA sub-study (as applicable), the data has been cleaned and the database locked and unblinding has occurred.

2.1. RESPONSIBILITIES

Veristat is the Biostatistics vendor for these studies and is contracted to prepare the table, figures and listing (TFLs) shells based on this SAP. Shells to detail the format and layout of TFLs will be presented in a separate document to the SAP. Veristat will perform the statistical analyses and is responsible for the production and quality control of all TFLs.

3. STUDY OVERVIEW

3.1. STUDY OBJECTIVES

The study objectives for REN001-201 are listed below in Sections 3.1.1 to 3.1.5. The objective for the REN001-201-DXA sub-study is listed in Section 3.1.6.

3.1.1. Primary Objective

To evaluate the efficacy of REN001 in subjects with PMM treated for 24 weeks, assessed by the effect on exercise endurance.

3.1.2. Secondary Objective

To evaluate the efficacy of REN001 in subjects with PMM treated for 24 weeks, assessed by the effect on fatigue.

3.1.3. Safety Objective

To evaluate the safety and tolerability of REN001 in subjects with PMM during 24 weeks of treatment.

3.1.4. Pharmacokinetic Objective

To investigate the pharmacokinetics of REN001 in subjects with PMM.

3.1.5. Exploratory Objectives

To evaluate the efficacy of REN001 in subjects with PMM treated for 24 weeks, assessed by the effect on functional capacity.

To evaluate the effect of REN001 on Quality of Life (QoL) of subjects with PMM after treatment for 24 weeks.

3.1.6. REN001-201-DXA Sub-Study Objective

To use DXA to supplement the bone health parameters already being assessed in a subset of PMM subjects who enter the parent REN001-201 STRIDE study.

3.2. STUDY ENDPOINTS

The study endpoints associated with the REN001-201 objectives detailed above in Section 3.1 are listed below in [Sections 3.2.1 to 3.2.5](#). The endpoints for the REN001-201-DXA sub-study are listed in [Section 3.2.6](#).

3.2.1. Primary Endpoint

Change from Baseline at Week 24 in distance walked during the 12-minute walk test (12MWT).

3.2.2. Secondary Endpoint

Change from Baseline at Week 24 in Patient-Reported Outcomes Measurement Information System (PROMIS) Short Form – Functional Assessment of Chronic Illness Therapy (FACIT) Fatigue 13a T-score.

Note, the secondary endpoint has been changed from the protocol (refer to [Section 14](#)).

3.2.3. Safety Endpoints

- Incidence and severity of adverse events (AEs)
- Absolute values, changes from Baseline and incidence of potentially clinically significant values for laboratory safety tests, electrocardiograms (ECGs), vital signs and eye assessments.

3.2.4. Pharmacokinetic Endpoints

Mavodelpar plasma concentrations collected pre-dose and 1, 2, 3 and 4 hours post-dose at Baseline, Week 12 and Week 24.

3.2.5. Exploratory Endpoints

- Changes from Baseline at Week 12 and 24 in:
 - number of sit to stands in 30 seconds using the sit to stand (STS) test
 - step count pedometer data
 - Patient Global Impression of Severity (PGIS) score for muscle symptoms and for fatigue symptoms
 - 36 Item Short Form Survey (SF-36) domain scores
 - MFIS Total, Physical, Cognitive and Psychosocial sub-scale scores
 - Brief Pain Inventory (BPI) Short Form pain severity and pain interference scores
 - Work Productivity and Activity Impairment questionnaire: Specific Health Problems (WPAI:SHP) scores
 - First 6-minute walk distance and last 6-minute walk distance*
 - Phenotypic description questions at Week 24 only*
- PGIC score for muscle symptoms and for fatigue symptoms at the end of treatment

- PGIC score for muscle symptoms and for fatigue symptoms responder (‘Very Much Improved’ or ‘Moderately Improved’) at the end of treatment*.

** Note these endpoints were not defined in the protocol.*

3.2.6. REN001-201-DXA Sub-Study Endpoints

Change from baseline to end of treatment in BMD, as measured by DXA, in the following:

- Lumbar spine (L1 to L4) BMD
- Total hip BMD and the femoral neck BMD (in the non-dominant hip)
- Total hip, lumbar spine, and femoral neck T-scores and Z-scores.

3.3. STUDY DESIGN

3.3.1. REN001-201 Study

REN001-201 is a pivotal global Phase 2b randomized, double-blind, placebo-controlled, parallel group, multi-center study in approximately 200 subjects with confirmed mtDNA PMM. Subjects will receive either mavodelpar 100 mg or matched placebo once daily for 24 weeks.

Each subject has a Screening visit to confirm eligibility to enter the study. The Screening visit must be completed within 8 weeks prior to the start of dosing and takes place at the study center. The Screening visit may be accomplished over more than 1 day. Subjects who are receiving prohibited medications for this study are required to suspend the medications and undergo sufficient washout during the screening period. Subjects may be re-screened once with prior approval from the Sponsor. An independent Patient Screening Oversight Committee (PSOC) assesses subjects to confirm the medical diagnosis of PMM prior to randomization.

Subjects who successfully complete screening, and are approved by the PSOC, are randomized to receive either mavodelpar or placebo. Subjects have study visits at Weeks 2, 4, 12, 18, 24 and, if applicable, follow-up. Visits at Weeks 2, 4, 18 and follow-up may be conducted at the subject’s home if more convenient and allowed by the site. Weeks 12 and 24 are completed at the study center. A follow-up visit is completed 21-28 days after the last dose of study medication. The follow-up visit is not required for subjects who enrol directly into the mavodelpar open label extension study (REN001-202) at their Week 24 visit. The schedule of assessments is detailed in [Section 3.4](#).

The planned maximum study duration for each subject is 36 weeks (assuming 8 weeks screening, 24 weeks treatment and 4 weeks follow up).

3.3.2. REN001-201-DXA Sub-Study

The REN001-201-DXA sub-study is an exploratory sub-study, designed to assess changes in BMD, using DXA scans, after 24 weeks of treatment with mavodelpar. Due to regulatory and/or Institutional Review Board/Institutional Ethics Committee (IRB/IEC) concerns of radiation exposure, some sites are not participating in the sub-study. For those sites where it is approved the sub-study is offered to all prospective REN001-201 study subjects aged 25 or above. Subjects who consent to this sub-study undergo 2 DXA scans to assess BMD. The first DXA scan is at baseline and performed during the REN001-201 screening period and the second follow-up DXA scan is performed at Week 24. If the subject discontinues treatment from REN001-201 after at least 20 weeks in the study, they will be asked to have a follow-up scan within 4 weeks of their last dose of study drug. Any subject who has not received 20 weeks dosing will not receive the follow-up DXA scan.

3.4. SCHEDULE OF ASSESSMENTS

Time and Events Table	Screening	Baseline ^{1,2} (Day 1)	Week 2 ³ (Day 14)	Week 4 ³ (Day 28)	Week 8 (Day 56)	Week 12 ^{2,4} (Day 84)	Week 16 (Day 112)	Week 18 ³ (Day 126)	Week 20 (Day 140)	Week 24 ^{2, 4} (Day 168).	Early Term ^{n,2,5}	Follow Up ³ (21-28 days post last dose)
Visit number	1	2	3	4		5		6		7		8
Window (days)			±3	±3		±7		±7		±7		
Informed Consent ²⁰	X											
Completion of Proforma and data entered into eCRF ⁶	X											
Demographics	X											
Medical/medication/drug/ alcohol/tobacco history ⁷	X											
Physician completion of PMM phenotypic description		X								X	X	
Physical exam ⁸	X	X				X				X	X	
12-lead ECG	X	X				X				X	X	
Supine Vital signs (BP, PR and temperature)	X	X	X	X		X		X		X	X	X
Serum FSH ⁹	X											
HbA1c	X									X	X	
Hepatitis B/C/HIV	X											
Safety labs (inc. urinalysis)	X	X ¹⁰	X	X		X		X		X ¹¹	X	X ¹¹
Blood sample for bone and calcium markers		X				X				X	X	
Pregnancy Test (WOCBP only) ¹²	X	X		X	X	X	X		X	X	X	X
Blood sample for genotyping ¹³	X											
Population PK blood sample ¹⁴		X	X	X		X		X		X	X	
Urine drugs of abuse	X	X				X				X	X	
Urine NTX		X				X				X	X	
Sites to provide appropriate snacks and lunch	X	X				X				X	X	

Time and Events Table	Screening	Baseline ^{1,2} (Day 1)	Week 2 ³ (Day 14)	Week 4 ³ (Day 28)	Week 8 (Day 56)	Week 12 ^{2,4} (Day 84)	Week 16 (Day 112)	Week 18 ³ (Day 126)	Week 20 (Day 140)	Week 24 ^{2, 4} (Day 168).	Early Termn ^{2,5}	Follow Up ³ (21-28 days post last dose)
Pedometer eDiary data collection (inc. review)	X	X ¹⁵		X		X		X		X		
MFIS / PGIS (muscle symptoms), PGIS (fatigue symptoms) and PROMIS – Short form FACIT fatigue 13a	X	X		X		X		X		X	X	
SF-36 / BPI and WPAI:SHIP		X		X		X		X		X	X	
PGIC (muscle symptoms) and PGIC (fatigue symptoms)										X	X	
12 Minute Walk Test	X ¹⁶	X				X				X	X	
30STS		X				X				X	X	
IMP Capsule Counts			X	X		X		X		X	X	
Eye examination	X ¹⁷					X				X	X	
Wrist radiograph	X ¹⁸											
DXA Scan (REN001-201-DXA sub-study) ²¹	X									X	X	
Concomitant medication review	X-----X											
Dosing		X ¹⁹ -----X										
AE collection and reporting	X-----X											

1. Screening visit must take place a maximum of 8 weeks before the Baseline visit.
2. If appropriate and feasible Baseline, Week 12, Week 24 /Early Termination visits may be conducted over 2 days at the Investigators discretion.
3. In countries where the regulatory body allows, visit may be in the Study Center or a home nursing visit.
4. Only review of concomitant medications, AE's MFIS and 12MWT will be conducted if the subject has discontinued from study drug treatment but has not withdrawn from the study. If the subjects had an ET visit within 2 weeks of either of these a visit is not required.
5. As a minimum, subjects should have review of concomitant medication and AE's, vital signs (including temperature), complete questionnaires, safety laboratory blood (including HbA1c, bone and calcium markers and PK analysis) and urinalysis (including pregnancy tests for WOCBP, drugs of abuse and NTX) and IMP capsule counts.
6. Patient Screen Oversight Committee will review Proforma data and give a decision or request more information within 7 working days.
7. Subjects will be excluded from the study at the Investigators discretion for alcohol and/or drug dependency. Use of opiates/cannabis for medical reasons is acceptable with prescription evidence or at the Investigators discretion.
8. Full physical exam, height and weight at Screening; full physical exam and weight at Baseline; brief, symptom-directed physical exam and weight only at Weeks 12 and 24.

9. Serum FSH testing for post-menopausal females 45 years and older. Serum FSH test must be performed for all women who participate in the REN001-201-DXA sub-study who have not already had an FSH test as part of the parent REN001-201 study.
10. An additional 10 mL blood sample will be taken pre-dose at baseline and the serum will be stored frozen at the central laboratory as a reference sample in the event that re-analysis of protocol stated tests are required.
11. If any clinically significant abnormalities are noted at the Week 24 visit, these should be followed up until resolved.
12. WOCBP will be supplied with urine home pregnancy test kits at Study Center visits to test at Weeks 8, 16 and 20. The Study Center must contact the subject to confirm the pregnancy test result in a timely manner.
13. Blood sample for local genotype testing will only be conducted with prior Sponsor approval and definitive results must be available prior to the Baseline visit.
14. At the Baseline, Week 12 and Week 24 visits, blood samples will be taken pre-dose and then at 1, 2, 3, and 4 hours post-dose. On the other visits, a single sample can be taken at any time post-dose provided the dosing date and time are recorded.
15. Review of Screening (pre-treatment) pedometer data at Baseline.
16. Screening 12MWT must be at least 4 weeks before the Baseline 12MWT.
17. The Screening eye examination can be performed at any time between the initial Screening and Baseline Visit for scheduling reasons.
18. Subjects <25 years old only.
19. Dosing on Baseline, Week 12 and Week 24 visits should be under the supervision of the site staff.
20. A separate informed consent will be required for the REN001-201-DXA sub-study.
21. Only conducted at sites, on eligible subjects, which are participating in the REN001-201-DXA sub-study. The screening DXA scan should be performed no more than 8 weeks prior to the start of dosing. If a subject discontinues study treatment after at least 20 weeks in the study they will be asked to have a follow-up, scan within 4 weeks of their last dose of study treatment.

3.5. DETERMINATION OF SAMPLE SIZE

A sample size of 186 subjects (93 per treatment group) provides 90% power, with a two-sided significance level of 5%, of obtaining a statistically significant difference between two treatment groups for the distance walked during the 12MWT. This assumes a treatment effect (difference versus placebo in mean change from baseline) size of 60 meters. The standard deviation for the changes from baseline observed in Study [REN001-101](#) was approximately 100 meters. A higher standard deviation, 125 meters, was assumed for this study due to the longer assessment period (24 weeks instead of 12 weeks) and the larger number of sites included in this study. Allowing for a reduction in power due to subject withdrawals, a total of approximately 200 subjects was determined as the appropriate sample size.

The sample size for the DXA sub-study is not based on statistical justification. This sub-study is exploratory in nature and limited to REN001-201 sites that have approval to conduct this sub-study.

3.6. TREATMENT ASSIGNMENT AND BLINDING

At Screening, all subjects are allocated a unique 6-digit study number by the Integrated Web-based Response System (IWRS), which is used throughout the study. The same subject identifier is used for both REN001-201 and REN001-201-DXA studies. The IWRS uses a computer-generated randomization schedule to assign subjects in a 1:1 allocation ratio to receive either mavodelpar 100 mg or placebo. The randomization is stratified by both mutational genotype (m.3243A>G or other mitochondrial DNA defects) and the screening 12-minute walk distance (≤ 500 meters or > 500 meters).

A subject may be rescreened once with prior Sponsor approval; they will be given a new study number (their original study number will be recorded).

To maintain the blind-blind conditions for the subject and Investigator, study medication is provided as visually matched capsules, and the capsules are supplied in identical bottles.

3.7. ADMINISTRATION OF STUDY MEDICATION

Subjects receive either 100 mg mavodelpar as 2 x 50 mg or placebo as 2 x placebo capsules for oral administration once daily for 24 weeks.

Medication should be taken with food, for consistency of exposure, at a convenient time to the subject (ideally in the morning). The exception to this is when the subject is required to attend the study center for their Baseline, Week 12 and Week 24 Visits, when they should take the study medication at the study center, when instructed to do so by the site staff. On these visits, sites will ensure the subjects take the study medication with food.

4. EFFICACY ASSESSMENTS

The sections below detail the efficacy assessments including any derivations required to define the efficacy endpoints. The analyses of these endpoints are detailed in [Section 10](#).

4.1. 12-MINUTE WALK TEST (12MWT)

The primary endpoint is the change from baseline in distance walked during the 12MWT at Week 24. Subjects will perform the 12MWT at Screening, Baseline, Week 12 and Week 24 visits. If applicable, the test will also be performed at the Early Termination visit.

The test measures the distance a subject can walk on a flat, hard surface in a period of 12 minutes. To reduce site variability, sites will be fully trained to administer the test according to the REN001-201 exercise manual. If the subject does not walk for the full 12 minutes, the distance walked and the duration of time walked will be recorded, along with the reason for stopping prematurely.

Handling of missing or incomplete 12MWT are detailed in [Section 8.3.1](#). An independent blinded adjudication committee will review all reasons for missing or incomplete 12MWTs and adjudicate whether the reason was related to the subject's PMM or study treatment.

Subjects who walk further than 1000 meters at Screening will be excluded from the study. Subjects who walk ≤ 1000 meters at Screening but subsequently walk greater than 1000 meters at Baseline will be allowed to continue into the study but will be excluded from the per protocol analysis. Baseline distance walked will be taken as the distance walked at the Baseline visit.

For each visit changes from baseline and percent changes from baseline will be calculated.

Additionally, the exploratory endpoints, distance walked in the first 6 minutes (from start of test up to 6 minutes) and the last 6 minutes (>6 minutes up to 12 minutes), will be derived. As only the number of completed laps are recorded each minute with the final minute recording any partial lap ongoing at the end of the 12 minutes, the distance walked in the first 6 minutes will be the total number of completed laps multiplied by the lap distance (20 meters). The distance walked in the last 6 minutes will then be the total distance walked minus the distance walked in the first 6 minutes. Note, in most cases, this will be an underestimate of the distance walked in the first 6 minutes and an over-estimate of the distance walked in the last 6 minutes.

Pre and post exercise measurements for heart rate and blood pressures are collected. The changes (post – pre) will be calculated.

4.2. PATIENT-REPORTED OUTCOMES MEASUREMENT INFORMATION SYSTEM (PROMIS) SHORT FORM – FUNCTIONAL ASSESSMENT OF CHRONIC ILLNESS THERAPY (FACIT) FATIGUE 13A

The PROMIS short form - FACIT Fatigue 13a is a set of person-centered measures that evaluates a range of fatigue symptoms, from mild subjective feelings of tiredness to an overwhelming, debilitating, and sustained sense of exhaustion that likely decreases a subject's ability to execute daily activities and function normally in family or social roles. The fatigue short forms are universal rather than disease specific. All assess fatigue over the past 7 days.

The PROMIS questionnaire will be used at Screening, Baseline, Week 4, Week 12, Week 18 and Week 24 visits. If applicable, the test will also be performed at the Early Termination visit.

There are 13 questions on a 5-point scale ranging from not at all (1) to very much (5). All questions, except Questions 7 and 8, are scaled so that higher score indicates a greater impact on fatigue. Questions 7 and 8 will be reversed prior to analysing. The total score is derived by summing the scores and will have a range from 13 to 65. If a subject has a missing response, then the total score will not be derived.

The T-score will be determined using the HealthMeasures Scoring Service (https://www.assessmentcenter.net/ac_scoringervice) (PROMIS 2019). This service uses "response pattern scoring" (Expected A Posteriori estimation) and will also derive a T-score when there is missing data. Subject ID and Visit will be de-identified in the dataset prior to using this scoring service. The T-score rescales the total score into a standardized score, relative to the US general population, with a mean of 50 and a standard deviation of 10. Therefore, an individual with a T-score of 60 is one standard deviation (SD) worse than the mean of the US general population.

For each visit changes from baseline will be calculated for the T-score and total score. The T-score is a secondary endpoint. The total score data will only be listed.

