8.2. GENERAL METHODS

All statistical testing will be at the 5% level of significance (2-sided) and all point estimates for the comparison between treatment groups will be accompanied by 2-sided 95% confidence intervals. To preserve the Type 1 error a fixed sequence testing procedure will be adopted. Testing will be on the FAS. The order of testing for the primary and secondary endpoints will be:

1. Change from Baseline at Week 24 in distance walked during the 12MWT
2. Change from Baseline at Week 24 in the PROMIS T-score

Continuous variables will be summarized using the number of non-missing observations (n), mean, SD, median, minimum, and maximum. Categorical variables will be summarized using counts and percentages.

Unless otherwise specified, the estimated mean and median for a set of values should be displayed to 1 more decimal place than the original values, and SD should be displayed to 2 more decimal places than the original values. The minimum and maximum should be displayed to the same number of decimal places as the original values. Deviations from this convention may arise to take account of the relevance of the precision (e.g., the distance walked in the 12MWT is reported to the nearest cm, but there is no relevance in presenting the mean to the nearest mm). These deviations from convention will be documented in the relevant analysis sections below.

Percentages will be displayed with 1 decimal place; except percentages will not be presented when the count is zero and 100% will be presented as an integer. Unless stated otherwise, percentages of subjects will be based on the number of subjects with non-missing data in the analysis set used for the presentation.

Baseline will be taken as the last available non-missing assessment prior to study drug administration (Day 1). Although the time of completion is not collected for QoL questionnaires (MFIS, PGIS, PROMIS, SF-36, BPI or WPAI:SHP), any completed on Day 1 will be deemed suitable for baseline as the questionnaires are requested in the protocol to

be completed prior to dosing and, even if after dosing, there is no anticipated effect after a single dose.

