If the subject is still ambulatory, and therefore able to do the test, then consideration should be given to whether the subject is unwilling to perform the test, or prevented from (e.g., specialty clinic visit that prevents attending the study visit) performing the test due to reasons possibly related to PMM or study treatment. If the subject is still ambulatory but unwilling to perform the 12MWT, or prevented from doing the test, their distance will be imputed using a worst case imputation; unless the reason is unrelated to PMM or study treatment. The change from baseline distance will be imputed using a random draw from the normal distribution with a mean equal to the worst change from baseline reported over the study across both treatment groups, and the standard deviation for the raw changes from baseline at the relevant visit irrespective of treatment group. These values will only be determined from those assessments where subjects have walked for the full 12 minutes (i.e., those assessments where there were no intercurrent events). Twenty-five imputations will be made to match the multiple imputations mentioned below for missing data. The imputations will be restricted to ensure the value for the visit is ≥ 0 meters for the visit.

The same approach as detailed above in the previous paragraph, will be taken for subjects who discontinue study treatment and do not continue in the study; unless the reason for discontinuing from the study and withdrawing from the study are unrelated to their PMM or study treatment (e.g., site unable to continue having visits during pandemic). The special exception to this will be death; if a subject dies their 12MWD will be imputed as 0 meters.

If the subject attempts the 12MWT or 30STS test but stops the test prematurely due to reasons at least possibly related to their PMM their data recorded will be used in all analyses. Examples of reasons for incomplete tests which will be considered related to the subject's PMM include fatigue, weakness, tiredness, exhaustion or pain in limbs. In this situation it is assumed that the subject has walked as far as they could in the 12 minutes and the data is not regarded as missing.

An independent blinded adjudication committee will review the 12MWT cases. The structure, function and operation of the adjudication committee will be detailed in a separate charter.

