	Unable to perform the test for reasons possibly related to PMM or study treatment. Subject is not ambulatory at time of assessment.	0
	Unable to walk the full 12 minutes for reasons possibly related to PMM or study treatment*	Use 12MWD recorded
	Ambulatory subject unwilling to, or prevented from, performing the test for reasons possibly related to PMM or study treatment	Worst case multiple imputation
	Withdrawal from study for reasons possibly related to PMM or study treatment	Worst case multiple imputation
	Death	0
Missing Data	Unable to perform the test, or walk the full 12 minutes, for reasons unrelated to PMM or study treatment e.g., COVID-19	Multiple imputation (MAR cases)
	Unwilling to perform the test for reasons unrelated to PMM or study treatment	
	Withdrawal from study unrelated to PMM or study treatment	

* Note: This is the only adjudication decision where the distance walked for subject’s unable to walk the full 12 minutes is used in the analyses. For all other decisions the distance is set to missing prior to analyses.

Multiple Imputation

Missing values will be imputed with the SAS[®] MI procedure. Prior to imputation the missing data pattern will be assessed. To account for non-monotone missingness (i.e., for the 12MWT this would be where a subject has missing data for Week 12, but has data for Week 24), a Markov Chain Monte Carlo (MCMC) model will be used to impute the non-monotone missing data, followed by a sequential regression model to impute the remaining data. Randomization seed numbers will be specified for each part of the imputation to ensure consistency and repeatability.

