The first and last 6-minute walk distances derived from the 12MWD will be analysed in the same way as the primary analysis. The model will include fixed terms for treatment, visit and the treatment-by-visit interaction. The model will also include the stratification mutation factor and continuous baseline distance walked during the 12MWT as covariates. The baseline 6-minute walk distance will not be included in the model as a covariate as this will be correlated with the baseline 12MWD already included in the model. Note that if a subject’s 12MWD is incomplete but they walk for longer than 6 minutes then only the last 6-minute period will be classified as incomplete and imputation rules applied. For example if a subject walks for 10 minutes and the walk is adjudicated as ‘ambulatory subject unwilling to, or prevented from, performing the test for reasons possibly related to PMM or study treatment’ then the worst case imputation will only apply to the last 6 minutes.

In addition to the summary presentation, mean plots for observed, change from baseline and percent change from baseline values, with 95% confidence intervals, will be presented by treatment group and 6-minute time period with visit on the x-axis. A reference line for no change (i.e., $y=0$) will be included in the change from baseline and percent change from baseline plots.

The first and last 6-minute walk distance values, mean, median, minimum and maximum will all be presented to 2 decimal places and SD will be presented to 3 decimal places.

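### For a walk that ends by minute 6, the SAP's 6-minute split can credit the unfinished lap to the last 6 minutes, and percent change for that distance has no rule for a zero or near-zero Baseline

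*SAP*

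**What the plan says.** SAP 4.1 derives two exploratory endpoints from the 12MWT: the distance in the first 6 minutes and the distance in "the last 6 minutes (>6 minutes up to 12 minutes"). Only whole laps are logged minute by minute, so "the distance walked in the first 6 minutes will be the total number of completed laps multiplied by the lap distance (20 meters"). The other half is obtained by subtraction: "The distance walked in the last 6 minutes will then be the total distance walked minus the distance walked in the first 6 minutes". The section notes that this usually understates the first half and overstates the second. It makes no exception for a walk that has already ended at minute 6.

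Four other statements bear on that case.

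- SAP 4.1, on early stops: "If the subject does not walk for the full 12 minutes, the distance walked and the duration of time walked will be recorded".
- SAP 8.3.1, on a subject who starts the walk and then "stops the test prematurely due to reasons at least possibly related to their PMM their data recorded will be used in all analyses". The table in that section extends this to stops possibly related to study treatment and adds: "For all other decisions the distance is set to missing prior to analyses".
- SAP 8.2, on resolution: "the distance walked in the 12MWT is reported to the nearest cm".
- SAP 10.3.9 deals with incomplete walks only where the subject got past minute 6. It plans "mean plots for observed, change from baseline and percent change from baseline values", with 95% confidence intervals, for each 6-minute period. It has no rule for a zero or near-zero Baseline.

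**The concern.** A subject who stopped at minute 4 walked nothing in the second half, yet the subtraction rule can give that subject a positive second-half distance. The SAP's caveat about under- and over-estimation does not justify this. It arises because the position at minute 6 is unknown for someone still walking. For a walk already over, all the distance belongs to the first half, and the recorded duration identifies the case.

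SAP 14 says the split is there to see whether the treatment effect differs between the two periods, so a false second-half distance bears on that purpose. The practical problem is percent change: a Baseline of a few metres, or of exactly zero, makes the individual percentage enormous or undefined, and a mean takes it in at full weight.

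**Working it through.** The documents give no computed figure for the split, so there is nothing to reproduce. The check applies the SAP 4.1 rule directly.

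**Inputs.** Lap length 20 m (SAP 4.1). Recorded distance is used for stops possibly related to PMM or study treatment (SAP 8.3.1). Distance is reported to the nearest cm (SAP 8.2). Assumed: the recorded total at an early stop includes the part lap. Also assumed, because the documents give no such values: a later last-6 distance of 50 m or 250 m, and an arm of 100 subjects (200 randomized 1:1).

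**Step 1: size of the artefact.** For a walk ending by minute 6, first-6 = 20 × (whole laps in the total) and last-6 = total − first-6. The true last-6 is 0 m throughout.

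| Stop (min) | Total (m) | First-6 by rule (m) | Last-6 by rule (m) |
|---|---|---|---|
| 4 | 120 | 120 | 0 |
| 4 | 121 | 120 | 1 |
| 4 | 130 | 120 | 10 |
| 4 | 139.99 | 120 | 19.99 |
| 5.5 | 205 | 200 | 5 |

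The error runs from 0 to just under 20 m. It averages about 10 m if stops fall uniformly within a lap (assumption). First-6 is understated by the same amount.

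**Step 2: comparison with full walkers.** For subjects who complete 12 minutes, the split error is also 0 to 20 m with mean about 10 m. At assumed speeds of 30 to 70 m/min, that mean is 5.6% to 2.4% of the last-6 distance. For the early stopper it is the whole of the value.

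**Step 3: absolute change.** An artefact of b metres at Baseline lowers that subject's change by b, and so lowers a 100-subject mean by b/100. That is 0.1 m at b = 10 and just under 0.2 m at the limit.

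**Step 4: percent change.** The formula is 100 × (later − Baseline)/Baseline. The contribution of one subject to a 100-subject mean is the result divided by 100.

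| Baseline last-6 (m) | Later 50 m | Later 250 m | Contribution to arm mean, 250 m case (percentage points) |
|---|---|---|---|
| 1 | +4,900% | +24,900% | 249 |
| 5 | +900% | +4,900% | 49 |
| 10 | +400% | +2,400% | 24 |
| 19.99 | +150% | +1,151% | 11.5 |

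If both walks end by minute 6, artefacts of 2 m and then 18 m read as 100 × (18 − 2)/2 = +800%, although the true change is 0 m. If the Baseline stop falls on a lap end, last-6 is 0 m and percent change is a division by zero.

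**Step 5: how often.** The documents do not say. A subject at the eligibility ceiling of 1000 m, walking evenly, covers 1000 × 6/12 = 500 m by minute 6. A Baseline walk ending by then would therefore normally fall in the group at or below 500 m, which SAP 10.1.5 describes as small on blinded review. Affected subjects are a subset of that group, possibly an empty one.

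**The case against.** Several points on the other side stand.

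- Part-lap capture at an early stop is inferred, not stated. SAP 4.1 mentions a part lap only at the end of the 12 minutes, and test conduct is left to the Exercise Manual, which is not among the documents. If part laps are not logged at early stops, last-6 is correctly 0 m. Percent change is then undefined, which the SAP still does not handle.
- The general direction of bias is disclosed, and its size in metres is the same as for full walkers. The disclosure does not say that for an early stop the error is avoidable.
- The percentages grow large only if the Baseline walk ended by minute 6 for a related reason and a later last-6 distance is much larger. Subjects must be able to do the test unaided by another person, and Protocol 3.3 allows rests during it, so tiring need not end a walk.
- The endpoint is exploratory and outside the testing sequence. Its model analyses absolute change with Baseline 12MWD as covariate, and percent change is descriptive. Medians, minima and maxima are also planned, so an extreme value would be visible.

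A reader might infer that one or two such Baselines will dominate the planned percent-change means. The documents give no frequency, so that is not supported. A reader might also infer that these subjects contribute nothing from the period of mitochondrial demand. Protocol 3.3 places its onset at roughly minute 4, so a stop at minute 5 does not imply that.

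**Conclusion.** The derivation rule is incomplete for walks that end by minute 6 and whose recorded distance is analysed. As written, it can return up to just under 20 m where the true last-6 value is 0 m. This rests on part laps being recorded at early stops. The effect on mean absolute change is negligible, and total 12MWD, the primary analysis and the testing sequence are unaffected.

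The percent-change display for the last 6 minutes is the weak point, and it is weak whether or not part laps are recorded: any Baseline at or near zero makes it undefined or unstable, including a genuine stop shortly after minute 6. How far it would be distorted in this trial cannot be stated, because the number of affected subjects is unknown and probably very small. This is a minor correction, worth making because it is almost free.

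**What to change.** In SAP 4.1, add that for tests whose recorded distance is used and whose recorded duration is 6 minutes or less, the first-6 distance equals the total distance and the last-6 distance is 0 m. Tests adjudicated as unrelated to PMM or study treatment stay missing under SAP 8.3.1. Without that limit, a walk aborted at minute 4 by a fire alarm would score 0 m.

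In SAP 10.3.9, drop percent change for the last-6 distance and report absolute change only. Reporting only the median percent change would not be enough, because the corrected derivation creates exact zeros at Baseline, for which the percentage does not exist.

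The cost is one line of derivation code, two short text edits and the loss of one descriptive display. No new data are needed.
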